2.0 Purpose

The objectives of the study are:

1. To determine the prevalence of externalized conductors at enrollment in Riata®, Riata® ST Silicone, QuickSite®/QuickFlex® and Durata® leads
2. To determine the prevalence of other visual lead anomalies by each subcategory per Appendix A at enrollment in Riata®, Riata® ST Silicone, QuickSite®/QuickFlex® and Durata® leads
3. To determine the prevalence of electrical dysfunction[§] at enrollment in Riata®, Riata® ST Silicone, QuickSite®/QuickFlex® and Durata® leads
4. To determine the incidence of externalized conductors after enrollment in Riata®, Riata® ST Silicone, QuickSite®/QuickFlex® and Durata® leads
5. To determine the incidence of other visual lead anomalies by each subcategory per Appendix A after enrollment in Riata®, Riata® ST Silicone, QuickSite®/QuickFlex® and Durata® leads
6. To determine the incidence of electrical dysfunction[§] after enrollment in Riata®, Riata® ST Silicone, QuickSite®/QuickFlex® and Durata® leads.
7. To evaluate the 30-day adverse event rate associated with lead revision procedures (include lead extractions or abandonments with or without lead replacement) in Riata®, Riata® ST Silicone, QuickSite®/QuickFlex®, and Durata® families of leads
8. To determine the prevalence of “other insulation anomalies” in “returned leads” for Riata®, Riata® ST Silicone, QuickSite®/QuickFlex®, and Durata® families of leads. “Other insulation anomalies” include any of the following:
 - Internal abrasion short under RV shock coil
 - Internal abrasion short under SVC shock coil
 - Exposed conductors defined as a breach of the outer insulation
 - Breach of the internal silicone lumen tubing, but the conductor cable is contained within the lead body diameter.

[§]”Electrical dysfunction” is determined to be present after adjudication of the following cases of potential electrical failures that led to the lead being either

surgically capped/extracted or electrically abandoned. Potential electrical failures include the following:

- Presence of non-physiologic noise not due to external interference
- Rise in pace/sense (p/s) conductor impedance to $> 2000 \Omega$ or increase of more than 200Ω over previous 6 months or increase of 400Ω over any period of time
- Decrease of more than 200Ω over previous 6 months or to impedance $< 200 \Omega$ from baseline impedance $> 300 \Omega$ or decrease of 400Ω over any period of time

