3.2.2 Secondary Outcome Measures

3.2.2.1 Time from enrollment to externalized conductors by lead subgroups

Lead Population

All the leads without externalized conductors at enrollment within the Riata, Riata ST silicone, QuickSite/QuickFlex (1056T, 1058T, 1156T, 1158) and Durata lead groups

Analysis:

Time to externalized conductors will be analyzed using the Kaplan-Meier method. Those patients who do not experience externalized conductors will be censored 3 years after enrollment in this trial. A separate Kaplan-Meier curve will be calculated for each of the lead subgroups outlined in Table 2.

For QuickSite/QuickFlex leads only, data from patients with an additional 1 year of follow-up will contribute to 2 separate lead subgroups (See Section 3.4.5).

3.2.2.2 Time from enrollment to other visual lead anomalies (evidenced by imaging) by lead subgroups and each subcategory

Lead Population

All the leads without other visual lead anomalies at enrollment (by each subcategory) within the Riata, Riata ST silicone, QuickSite/QuickFlex (1056T, 1058T, 1156T, 1158) and Durata lead groups

Analysis:

Time to other visual lead anomalies (by each subcategory) will be analyzed using the Kaplan-Meier method. Those patients who do not experience other visual lead anomalies (by each subcategory) will be censored 3 years after enrollment in this trial. A separate Kaplan-Meier curve will be calculated for each of the lead subgroups outlined in Table 2.

For QuickSite/QuickFlex leads only, data from patients with an additional 1 year of follow-up will contribute to 2 separate lead subgroups (See Section 3.4.5).

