3.2.2.3 Time from enrollment to electrical dysfunction, by lead subgroups**Lead Population**

All the leads without electrical dysfunction at enrollment within the Riata, Riata ST silicone, QuickSite/QuickFlex (1056T, 1058T, 1156T, 1158) and Durata lead groups

Analysis:

Time to electrical dysfunction will be analyzed using the Kaplan-Meier method. Those patients who do not experience an electrical dysfunction will be censored 3 years after enrollment in this trial. A separate Kaplan-Meier curve will be calculated for each of the lead subgroups outlined in Table 2.

For QuickSite/QuickFlex leads only, data from patients with an additional 1 year of follow-up will contribute to 2 separate lead subgroups (See Section 3.4.5).

3.2.2.4 Time from externalized conductors to electrical dysfunction, by lead subgroups**Lead Population**

All the leads with externalized conductors but without electrical dysfunction within the Riata, Riata ST silicone, QuickSite/QuickFlex (1056T, 1058T, 1156T, 1158) and Durata lead groups

Analysis:

Time to electrical dysfunction will be analyzed using the Kaplan-Meier method. The zero time will be the date at which externalized conductor was detected. Those patients who experience an externalized conductor after enrollment, but do not experience an electrical dysfunction will be censored 3 years after enrollment in this trial. A separate Kaplan-Meier curve will be calculated for each of the lead subgroups outlined in Table 2.

For QuickSite/QuickFlex leads only, data from patients with an additional 1 year of follow-up will contribute to 2 separate lead subgroups (See Section 3.4.5).

3.2.2.5 Time from other visual lead anomalies by each lead subcategory to electrical dysfunction, by lead subgroups**Lead Population**

All the leads with other visual lead anomalies (by each subcategory) but without electrical dysfunction within the Riata, Riata ST silicone, QuickSite/QuickFlex (1056T, 1058T, 1156T, 1158) and Durata lead groups

Analysis:

Time to electrical dysfunction will be analyzed using the Kaplan-Meier method. The zero time will be the date at which other visual lead anomaly (by each subcategory) was detected. Those patients who experience other visual lead anomaly (by each subcategory) after enrollment, but do not experience an electrical dysfunction will be censored 3 years after enrollment in this trial. A separate Kaplan-Meier curve will be calculated for each of the lead subgroups outlined in Table 2.

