3.2.2.7 Time from externalized conductors to clinical intervention

Lead Population

All the leads with externalized conductors within the Riata, Riata ST silicone, QuickSite/QuickFlex (1056T, 1058T, 1156T, 1158), and Durata lead groups

Analysis:

Time to clinical intervention will be analyzed using the Kaplan-Meier method. The zero time will be the date at which externalized conductor was detected. Those patients who experience externalized conductor after enrollment but do not experience clinical intervention will be censored 3 years after enrollment in this trial. A separate Kaplan-Meier curve will be calculated for each of the lead subgroups outlined in Table 2.

For QuickSite/QuickFlex leads only, data from patients with an additional 1 year of follow-up will contribute to 2 separate lead subgroups (See Section 3.4.5).

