3.2.2.8 Time from other visual lead anomalies by each subcategory to clinical intervention

Lead Population

All the leads with other visual lead anomalies (by each sub category) within the Riata, Riata ST silicone, QuickSite/QuickFlex (1056T, 1058T, 1156T, 1158), and Durata lead groups

Analysis:

Time to clinical intervention will be analyzed using the Kaplan-Meier method. The zero time will be the date at

which other visual lead anomaly (by each subcategory) was detected. Those patients who experience other visual lead anomaly (by each subcategory) after enrollment but do not experience clinical intervention will be censored 3 years after enrollment in this trial. A separate Kaplan-Meier curve will be calculated for each of the lead subgroups outlined in Table 2.

For QuickSite/QuickFlex leads only, data from patients with an additional 1 year of follow-up will contribute to 2 separate lead subgroups (See Section 3.4.5).

3.2.2.9 Comparison of patients with lead compromise as evidenced by imaging (includes externalized conductors and other visual lead anomalies by each subcategory) to those without lead compromise

Patient Population

All the patients within the Riata, Riata ST silicone, QuickSite/QuickFlex (1056T, 1058T, 1156T, 1158) and Durata lead subgroups.

Analysis

Demographic and clinical parameters will be compared between patients who experience a lead compromise as evidenced by imaging and those who do not experience a lead compromise. Specifically, the variables age, gender, body mass index, lead size, lead model, and implant factors such as venous access site, number of other leads in the vasculature, fixation location in the right ventricle, level of activity (based on functional NYHA class scale I, II, III, IV), level of therapy that patient received (no ATP/shock, ATP or shock) and slack (grades 0, 1, 2, 3, 4 based on the scale described by Ha et al., 2010¹²) in the lead will be used for the comparison. Continuous variables such as age or body mass index will be compared using Student's T-tests while categorical variables such as gender or lead models will be compared using Pearson's Chi-square statistic. Point estimates and p-values will be provided from these analyses.

3.2.2.10 Comparison of patients with electrical dysfunction to those without electrical dysfunction.

Patient Population

All the patients within the Riata, Riata ST silicone, QuickSite/QuickFlex (1056T, 1058T, 1156T, 1158) and Durata lead subgroups.

Analysis

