Demographic and clinical parameters will be compared between patients who experience electrical dysfunction and those who do not experience electrical dysfunction. Specifically, the variables age, gender body mass index, lead size, lead model, and implant factors such as venous access site, number of other leads in the vasculature, fixation location in the right ventricle, level of activity (based on functional NYHA class scale I, II, III, IV), level of therapy that patient received (no ATP/shock, ATP or shock) and slack in the lead (grades 0, 1, 2, 3, 4 based on the scale described by Ha et al, 2010¹²) will be used for the comparison. Continuous variables such as age or body mass index will be compared using Student's T-tests while categorical variables such as gender or lead models will be compared using Pearson's Chi-square statistic. Point estimates and p-values will be provided from these analyses.

In addition, the two patient groups will be compared for the following endpoints:

1. Frequency of externalized conductors. This will be done using a Pearson's Chi-square analysis.
2. Frequency of other visual lead anomalies. This will be done using a Pearson's Chi-square analysis.
3. Time to detection of externalized conductors. A Kaplan-Meier analysis will be used for this comparison.
4. Time to detection of other visual lead anomalies. A Kaplan-Meier analysis will be used for this comparison.
5. The extent of externalization will be compared using Pearson's Chi-square analysis.
6. Number of zones with externalization within one lead will be compared using a Student's T-test.
7. Location of externalization will be compared using Pearson's Chi-square analysis.
8. Amount of slack in the lead (based on the scale described by Ha et al, 2010)¹² will be compared using Pearson's Chi-square analysis.

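### Seven secondary Kaplan-Meier outcomes state one per-patient censoring time, 3 years after enrollment, which as written mishandles early loss, removed leads, leads abnormal at enrollment and the 48-month cohort

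*Combined protocol and SAP*

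**What the plan says.** The combined protocol and SAP uses Kaplan-Meier for seven secondary outcomes that state a censoring time, and it is always the same one.

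- **Time from enrollment (3.2.2.1 to 3.2.2.3).** For externalized conductors: "Those patients who do not experience externalized conductors will be censored 3 years after enrollment in this trial". For electrical dysfunction: "Those patients who do not experience an electrical dysfunction will be censored 3 years after enrollment in this trial". Section 3.2.2.2, on other visual anomalies, is worded in parallel.
- **Time from detection of an anomaly (3.2.2.4, 3.2.2.5, 3.2.2.7, 3.2.2.8).** The population in 3.2.2.4 begins "All the leads with externalized conductors but without electrical dysfunction within the Riata" and goes on to name the other lead groups; it is not limited to new cases. The censoring sentence is: "Those patients who experience an externalized conductor after enrollment, but do not experience an electrical dysfunction will be censored 3 years after enrollment". Section 3.2.2.7 has "Those patients who experience externalized conductor after enrollment but do not experience clinical intervention will be censored 3 years after enrollment in this trial", 3.2.2.8 has "Those patients who experience other visual lead anomaly (by each subcategory) after enrollment but do not experience clinical intervention will be censored 3 years", and 3.2.2.5 follows the same pattern.
- **Group comparisons (3.2.2.10, items 3 and 4).** "A Kaplan-Meier analysis will be used for this comparison", with no censoring time given.

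Section 3.1 sets three years of follow-up, and Table 2 expects 37% to 47% attrition by then. Sections 3.4.3 and 9.0 withdraw a patient after a lead is removed or abandoned only if no other study lead remains. Section 3.4.5 and Table 5 let QuickSite/QuickFlex patients with an extra year contribute to a second age cohort, with baseline at month 12 and data to month 48.

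**The concern.** A Kaplan-Meier curve is only as good as its risk sets. In 3.2.2.1 to 3.2.2.3 the sentence covers every event-free patient without exception. A programmer who follows it would leave a lead lost at month 4 at risk until month 36. With no earlier censoring, the Kaplan-Meier estimate at 3 years is simply events divided by leads, and events that could not be observed after loss count as non-events. The error makes leads look more durable than they are, which is the unfavourable direction for a post-market study of lead failure.

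The sentence also leaves analysts to invent rules for leads removed from continuing patients, leads already abnormal at enrollment, and the second QuickSite/QuickFlex cohort. Two competent analysts could then draw different curves from the same data. The outcomes timed from detection serve a stated aim of section 1.0: whether externalized conductors with normal function may progress to electrical malfunction.

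**Working it through.** **1. The plan's attrition figures (section 3.1) reproduce.**
- Mortality mix: 0.6 × 0.20 + 0.4 × 0.337 = 0.2548, stated as 25.5%.
- High-voltage leads: 1 − 0.745 × 0.85 = 36.7% (stated 37%).
- Riata/Riata ST: 1 − 0.745 × 0.85 × 0.90 = 43.0% (stated 43%).
- Left ventricular leads: 1 − 0.663 × 0.85 = 43.6% (stated 43.6%).

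**2. Leads affected if the sentence is applied as written.** Table 2 target × attrition:
- Riata under 6 years: 180 × 0.43 = 77.
- Riata 7 years or more: 195 × 0.47 = 92.
- Each Durata subgroup: 275 × 0.37 = 102.
- QuickSite/QuickFlex under 5 years: 300 × 0.44 = 132.

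**3. Size of the shortfall, 3.2.2.1 to 3.2.2.3.** The documents give no event rate, so I assume a constant hazard h of 1%, 2% or 5% per year, and loss at a constant rate d = −ln(1 − A)/3, independent of the event, where A is 3-year attrition.
- Net 3-year risk (no lead lost): 1 − exp(−3h).
- As-written estimate, electrical: h/(h + d) × [1 − exp(−3(h + d))].
- As-written estimate, imaging at 12, 24 and 36 months: Σ over k = 1, 2, 3 of [exp(−h(k − 1)) − exp(−hk)] × exp(−dk).

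Worked case, A = 0.43 and h = 0.02, so d = 0.1874:
- Net risk: 1 − exp(−0.06) = 5.82%.
- Electrical: (0.02/0.2074) × [1 − exp(−0.622)] = 0.0964 × 0.463 = 4.47%, a shortfall of 23%.
- Imaging: 0.0164 + 0.0133 + 0.0108 = 4.06%, a shortfall of 30%.

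| Attrition | Electrical shortfall, h = 1–5% | Imaging shortfall, h = 1–5% |
|---|---|---|
| 37% | 19.5–19.8% | 25.5–25.9% |
| 43% | 23.0–23.4% | 30.0–30.4% |
| 47% | 25.4–25.9% | 33.1–33.4% |

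**4. Sensitivity.**
- *Timing of loss.* All loss in the last 18 months: 9–13% (electrical) and 16–22% (imaging). All loss in the first 18 months: 27–36% and 33–43%.
- *Death as competing.* The target becomes the same formula with d replaced by the death rate alone. With death at 25.5% and other loss at 15% plus 10% (Riata), h = 0.02: electrical 5.05% against 4.47%, a shortfall of 11.6%; imaging 4.81% against 4.06%, 15.5%. Across the section 3.1 rates the ranges are 7–12% and 10–16%. With Riata explant also competing they fall to about 7% and 10%.
- *Extra images.* Cines outside the annual schedule (11.2) would move the imaging figures toward the electrical ones.

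**5. Outcomes timed from detection.** Time at risk up to 3 years after enrollment differs by lead, so the estimate does not collapse to events divided by leads. Keeping lost leads at risk still biases downward; I have not sized it.

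**6. Patient rule, lead curves.** Section 3.3.1 admits patients with one or more eligible leads. Under 3.4.3 and 9.0, a patient who loses one study lead and keeps another stays in the study. Under a per-patient time the removed lead stays at risk. For electrical dysfunction, a lead being "surgically capped/extracted or electrically abandoned" for an adjudicated electrical failure is part of the event (2.0), so the gap concerns removal for other reasons. Section 3.1 expects such removals: it allows an extra 10% of Riata/Riata ST withdrawals for explants that may occur with normal function. The number of patients with two study leads is not given, so this is not sized.

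**7. The 48-month cohort.** A lead re-based at month 12 reaches 3 years at month 48. Censoring 3 years after enrollment in the trial stops it at month 36, its second year, although the same outcome sections (all seven) say the extra year contributes.

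**8. Censoring imaging leads at the actual date of the last cine.** Simulating the worked case (true 5.8%) with visits placed in different parts of the ±60-day window (Table 4), the curve read at 36 months ranged from 4.5% (visits at 0 to +60 days) to 6.8% (−60 to +20 days). Assigning each cine to its nominal annual visit gave 5.7–6.0%.

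**The case against.** The strongest reply is that the sentence only marks the end of planned follow-up. Kaplan-Meier exists to handle unequal follow-up, three years is the planned duration (3.1, 3.4.1), section 9.0 defines withdrawal as the end of participation, and Table 2 inflates enrollment for losses. A competent statistician would probably censor lost leads at last follow-up without being told. This stands as the likely intent, and it makes every figure above conditional on the text being applied as written. It does not make the text correct: no earlier censoring time appears anywhere in the document.

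It can also be said that the populations are defined by lead, so the word patients is loose and a removed lead naturally leaves its own risk set. That is reasonable, but falling back on the patient's last follow-up would not achieve it. The reply is strongest for 3.2.2.7 and 3.2.2.8, where removal is probably the event: 3.2.2.6 lists extraction and abandonment as interventions, although the term is not defined for those two outcomes. The removed-lead gap is therefore confined to 3.2.2.1 to 3.2.2.5.

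For leads abnormal at enrollment, three-year follow-up is the only end point on offer, so the omission is a wording gap more than a source of large error. For the second QuickSite/QuickFlex cohort, Table 5 places its month-12 data in the enrollment/baseline column, which suggests a re-based clock; the censoring sentence does not adopt it.

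Finally, these are descriptive secondary curves with no test or power calculation attached. That limits the consequence, not the need for a correct rule.

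**Conclusion.** The concern holds as a defect in a stated rule for secondary outcomes and should be fixed before analysis. If the sentence is followed as written in 3.2.2.1 to 3.2.2.3, net 3-year risk is understated by about 20–26% (electrical) or 26–33% (annual imaging), and by about 7–16% if death is treated as competing. These figures rest on assumed hazards of 1–5% per year, the plan's own attrition, and steady loss independent of the event; other loss patterns widen the range. The gaps for removed leads (3.2.2.1 to 3.2.2.5), for leads abnormal at enrollment (3.2.2.4, 3.2.2.5, 3.2.2.7, 3.2.2.8) and for the 48-month cohort are textual and not sized.

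A reader might infer more than the documents support:
- *That the analysis will be biased.* End-of-study censoring is the more likely intent.
- *That leads lost early have no censoring time at all.* In 3.2.2.1 to 3.2.2.3 the literal text gives them one; the trouble is that it is too late.
- *That the primary results are affected.* The annual hazard rates in 3.2.1.4 to 3.2.1.6 are not governed by this sentence.
- *That all seven curves reduce to events divided by leads.* Only the three timed from enrollment do.

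**What to change.** Replace the censoring sentence in all seven outcomes with:

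> Each lead without the event, including leads already abnormal at enrollment, is censored at the earliest of its last evaluable assessment, death, withdrawal, removal of that lead where removal is not part of the event, or the 36-month visit (48-month visit for the re-based second QuickSite/QuickFlex cohort).

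For each outcome, state whether removal counts as the event. Apply the same rule to the Kaplan-Meier comparisons in 3.2.2.10.

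For imaging outcomes, require that each adjudicated cine be assigned to its nominal annual visit, or analyse the data as interval-censored. This is needed because an actual-date curve read at 36 months depends on where visits fall in the window. A competing-risk sensitivity analysis is optional.

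The cost is one sentence and a little programming on data the case report forms already collect (follow-up visits, system revision, product out of service, withdrawal, death). Compared with literal use of the present text, estimates become less favourable and less precise: at a true 5.8% in a 180-lead subgroup with 43% attrition, simulation puts the standard error at about 2.0 percentage points instead of 1.5. No visit, procedure or enrollment target changes.

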3.4.1 Enrollment

Upon determination of study eligibility, informed consent will be obtained from eligible patients by the principal investigator or designee prior to initiation of any study related screening activities.

Patients with Riata, Riata ST, QuickSite (1056T or 1058T), QuickFlex (1156T or 1158T), and Durata leads with model numbers and lead implant dates indicated in Table 1 will be screened for evidence of externalized conductors or other visual lead anomalies through cinefluoroscopy that will include three videos/cines of the entire lead length as well as the pocket area (AP, LAO 45° or best possible LAO, RAO 45° or best possible RAO). A copy of Cinefluoroscopy performed as part of separate screening can be used to determine the incidence of externalization as long as all three views (AP, LAO 45° or the best possible LAO view, RAO 45° or the best possible RAO view) are available. Patients who underwent cinefluoroscopy at enrollment as part of the “Riata Lead Evaluation Study” will not be required undergo another baseline cinefluoroscopy. In patients with evidence of externalized conductors, the following chest x-rays will be collected, if available: a) earliest chest x-ray or imaging study showing an evidence of externalized conductors or other visual lead anomalies and b) latest chest x-ray or imaging study that does not show any evidence of externalized conductors or other visual lead anomalies.

Data will be collected on the patient demographics (gender, age, medical history, history of electrical dysfunctions in the past, etc). Lead electrical performance will also be evaluated.

For the purposes of this study, a patient is considered enrolled upon signing of the consent form and collection of data at enrollment visit. Data previously collected from patients enrolled in other ongoing SJM registries may be used for this study.

Data to be captured at enrollment includes:

- RV lead capture threshold, lead pacing impedance and signal amplitude (only required if RV lead model and implant date is listed in Table 1)*
- LV lead capture threshold, lead pacing impedance in a bipolar configuration (only required if LV lead model and implant date is listed in Table 1)
- High Voltage Lead impedance (HVLI) testing – mandatory for Current/ Promote or later ICD and CRT-D, optional for devices before Current/Promote ICD and CRT-D, and not applicable to CRT-P

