3.4.5 Extended Follow-up (Eligible QuickSite/QuickFlex patients only)

The purpose of extending follow-up for eligible patients with QuickSite/QuickFlex leads is to address challenges with fulfilling the minimum number of leads to enroll for the QuickSite/QuickFlex lead group/subgroups as shown in Table 2.

The extended follow-up will help address this issue since the data from patients with extended follow-up will contribute to 2 separate sub-group cohorts for the primary and secondary outcome measure analyses.

For example, a patient who was enrolled with a QuickSite/QuickFlex lead that was implanted for 5 years at the time of enrollment will contribute to the ≥ 5 to <6 year age of lead subgroup cohort (data from lead 5, 6, 7, and 8 years implanted). After this patient provides consent and completes the additional year of follow-up, this patient will also contribute to the ≥ 6 year age of lead subgroup cohort (data from lead 6, 7, 8, and 9 years implanted) as shown in Table 5 below.

Table 5: Extended Follow-Up Example

QS/QF Subgroup cohort Age of Lead @ Enrollment	Primary and Secondary Outcome Measure Data Analyses Timepoints				Extended Follow-up
	Enrollment /Baseline	12 Mo. Visit	24 Mo. Visit	36 Mo. Visit	
≥ 5 and <6 year	5 yr. lead data	6 yr. lead data	7 yr. lead data	8 yr. lead data	9 yr. lead data
≥ 6 year	6 yr. lead data	7 yr. lead data	8 yr. lead data	9 yr. lead data	

Patients eligible for extended follow-up are those already enrolled with QuickSite/QuickFlex leads that have not previously withdrawn and have a QuickSite/QuickFlex lead that will contribute to a second subgroup cohort with an additional year of follow-up.

In order to maintain an unbiased study design, all eligible patients will be approached to provide consent for extended follow-up. SJM will provide study sites with a list of all eligible patients upon approval of this protocol. After eligible patients have been approached to consent for extended follow-up, complete the Extended Follow-Up Consent CRF using the EDC system.

Eligible patients must provide consent for extended follow-up prior to completing the 42 and 48 month follow-up visits (See Section 14.0). Refer to Table 3 and Section 3.4.2 for the requirements for these additional follow-up visits.

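### The Kaplan-Meier rule that censors event-free patients 3 years after trial enrollment cuts off the extension year that Table 5 assigns to the second QuickSite/QuickFlex cohort

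*Combined protocol and SAP*

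**What the plan says.** Section 3.2.2.1 (time to externalized conductors) states: "Those patients who do not experience externalized conductors will be censored 3 years after enrollment in this trial". Section 3.2.2.3 has the same rule for electrical dysfunction: "Those patients who do not experience an electrical dysfunction will be censored 3 years after enrollment in this trial". Sections 3.2.2.2, 3.2.2.4, 3.2.2.5, 3.2.2.7 and 3.2.2.8 repeat it; in 3.2.2.7, for example, patients who "do not experience clinical intervention will be censored 3 years after enrollment in this trial". In 3.2.2.4, 3.2.2.5, 3.2.2.7 and 3.2.2.8 the clock starts at detection of the anomaly (3.2.2.4: "The zero time will be the date at which externalized conductor was detected"), and the rule is worded for anomalies found after enrollment.

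Each of the seven sections then adds, for QuickSite/QuickFlex only, that "data from patients with an additional 1 year of follow-up will contribute to 2 separate lead subgroups" and refers to Section 3.4.5. That section takes a lead aged 5 years at enrollment and, after the extra year, also places it in the cohort aged 6 years or more, with "data from lead 6, 7, 8, and 9 years implanted". Table 5 puts the 6-year data in that cohort's baseline column and the 9-year data in its 36-month column.

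Section 3.4.1 defines enrollment once: "a patient is considered enrolled upon signing of the consent form and collection of data at enrollment visit". Section 3.4.2 counts the visit schedule from that date and adds cinefluoroscopy at month 48 for extended patients.

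**The concern.** The extension was added because the QuickSite/QuickFlex subgroups were hard to fill, and its yield is one more year of data in an older age cohort. The censoring sentence falls before that year and has no exception for extended leads. Because it names only patients without the event, two programmers could follow it and produce different curves: one cuts every lead at month 36, the other keeps events found up to month 48 while event-free leads have already left the risk set. Neither gives the curve that Table 5 describes. At stake is the third year of the second-cohort curves, for which patients consent to two more visits and a further fluoroscopy.

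**Working it through.** **1. The plan's own timeline.** In the example, lead age = 5 + month/12.

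| Trial month | Lead age (years) | Second-cohort month |
|---|---|---|
| 12 | 6 | 0 |
| 24 | 7 | 12 |
| 36 | 8 | 24 |
| 48 | 9 | 36 |

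This reproduces Table 5. A cut at trial month 36 takes 36 − 24 = 12 of 36 months (33.3%) from each event-free extended lead. If the plan's attrition for left ventricular leads is spread evenly (yearly retention 0.872 × 0.85^(1/3) = 0.826, so 0.826² = 0.682 and 0.826³ = 0.564), year 3 still holds 1 − (1 − 0.682)/(1 − 0.564) = 27% of expected cohort lead-time.

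**2. Sections 3.2.2.1 to 3.2.2.3, mixed cohort.** The cohort size of 115 is the Table 2 minimum for leads aged 6 years or more. Assumed, because the documents do not give them: hazard 3% per year, 30% loss over 3 years, extended share p of 25%, 50% or 75%, and detection at annual imaging.

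- Per-year event probability: h = 1 − exp(−0.03) = 0.0296. Aligned 3-year risk: 1 − exp(−0.09) = 8.6%.
- Events kept, event-free extended leads censored at month 36: the year-3 risk set holds the non-extended leads plus only those extended leads that have the event. The year-3 probability becomes h/[(1 − p) + p·h]. For p = 0.5 this is 0.0296/(0.5 + 0.0148) = 0.0574, and the 3-year risk is 1 − 0.9418 × 0.9426 = 11.2%, where 0.9418 = exp(−0.06). For p = 0.25 and 0.75 the formula gives 9.5% and 16.1%.
- Simulation of 4,000 cohorts per scenario agrees:

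| Extended share | Aligned | Events kept, event-free cut | One cut for all | At risk, year 3: aligned → one cut | Standard error, points: aligned → one cut |
|---|---|---|---|---|---|
| 25% | 8.6% | 9.4% | 8.6% | 76 → 58 | 2.9 → 3.1 |
| 50% | 8.6% | 11.1% | 8.6% | 76 → 38 | 2.9 → 3.5 |
| 75% | 8.6% | 15.8% | 8.6% | 76 → 19 | 2.9 → 4.4 |

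The relative overstatement in the third column is about +10%, +30% and +83%.

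**3. Limiting case.** Take 115 completers, all extended, with an assumed 2 events at each annual visit.

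- Aligned: 6 events in 2·1 + 2·2 + 111·3 = 339 lead-years; 3-year survival (113/115)(111/113)(109/111) = 0.948.
- One cut for all: 4 events in 2·1 + 2·2 + 111·2 = 228 lead-years; the curve ends at cohort month 24 at 0.965.
- Events kept, event-free cut: 6 events in 2·1 + 2·2 + 2·3 + 109·2 = 230 lead-years, or 2.61 against 1.77 per 100 lead-years. Only the 2 event leads are at risk at cohort month 36, so the estimate falls to 0.

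**4. Sections 3.2.2.4, 3.2.2.5, 3.2.2.7 and 3.2.2.8.** Time zero is detection, so step 2 does not apply. For a lead followed to month 48 without the later event:

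| Detected at month | Follow-up as written | Follow-up to month 48 |
|---|---|---|
| 24 | 36 − 24 = 12 | 24 |
| 36 | 0 | 12 |
| 48 | 36 − 48 = −12 | 0 |

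The rule discards up to 12 months, and gives a negative time for any anomaly first detected after month 36.

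**The case against.** The best defence is that each section sends these leads to Section 3.4.5, and that Table 5, whose heading covers the secondary outcomes, places the 9-year data in the second cohort's 36-month column. On that view, 3 years after enrollment means 3 years after the cohort's own baseline, and the sentence is base-design text that was not updated. The intent is probably just that. But the rule says enrollment in this trial, enrollment is defined once, visits run from it, and no section gives the second cohort its own time zero or censoring date. The month-12 clock has to be inferred from Table 5, so the conflict stands.

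Three limits on scope also stand. The month-12 clock and the simulated bias apply to 3.2.2.1 to 3.2.2.3 only. The inflation needs the branch that keeps late events while censoring event-free leads; no section instructs this, and naming only event-free patients is the usual way to state administrative censoring. The simulation inputs are also illustrative: Table 2 expects 46% attrition in this subgroup, and Section 3.4.5 admits a lead to the second cohort only once the extra year is completed.

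A reader might infer that the primary hazard rates lose the extension year too. The documents do not support that: 3.2.1.4 to 3.2.1.6 state no censoring rule and do refer to Section 3.4.5.

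**Conclusion.** The rule as written conflicts with Section 3.4.5 and Table 5 and should be corrected before analysis. In 3.2.2.1 to 3.2.2.3 it ends event-free follow-up at month 24 of a 36-month cohort clock. The consequence depends on a choice that the plan leaves open. One cut for all leads gives no bias, but wider uncertainty at year 3 (standard error 2.9 rising to between 3.1 and 4.4 points). Keeping late events alone overstates the 3-year risk (8.6% becoming about 9.4% to 15.8%). Both ranges assume a 3% yearly hazard, 30% loss and 25% to 75% extended leads. In the four detection-based analyses the fault is confined to the month-36 cut; no bias of this size is shown for them.

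It would go too far to read this as a certain inflation of all seven outcomes, or as a loss of everything that extended leads add: months 12 to 36 still enter the older cohort under either reading.

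**What to change.** 1. In 3.2.2.1 to 3.2.2.3, add: *For the second cohort of an extended QuickSite/QuickFlex lead, time zero is the 12-month visit; leads with the event at or before that visit are excluded from that cohort's event-free population; follow-up ends, for leads with and without the event alike, at the earlier of last follow-up and the 48-month visit.*
2. In 3.2.2.4, 3.2.2.5, 3.2.2.7 and 3.2.2.8, keep the detection date as time zero. End the second cohort's follow-up at the earlier of last follow-up and the 48-month visit, and state how a lead whose anomaly was detected at or before month 12 is handled in that cohort.
3. For the first cohort, apply the 36-month cut, or last follow-up if earlier, to events and event-free leads alike.

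The cost is protocol and SAP wording. The 42- and 48-month data are already to be collected, so no visit, imaging or enrollment changes.
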